respectively, and the limit of detection was 1 pg for both. With participant consent, DNA will also be obtained for future analysis. Plasma samples for DNA will be coded and sent to UT Southwestern McDermott Center for Human Growth and Development. Samples will have their DNA banked in a secure freezer with coded identification that will not include any personal identifiers such as the subject's name. Samples will begin to be analyzed when 50% (100) have been collected. When candidate genes have been suitably refined, and SNP chips become commercially available, appropriate pathways and candidate genes will be assessed via SNP chips and associated with previously assessed behaviors, personality styles, and/or biologic responses. *The neurosteroid and choline levels are essential as biomarkers and predictor of clinical response, as well as to address exploratory aim 5.*

3.3.c. Statistical Analyses Plan

Randomization: A statistician will randomize participants, stratifying by baseline drinks per drinking day of ≥ 8 and < 8 (based on use patterns in our prior studies).

General Analytic Plan: This is a study utilizing a two-stage adaptive trial design with one planned interim analysis (at end of the first stage). Two stages consist of a treatment selection stage (Stage 1) and a stage of early efficacy confirmation of the selected treatment(s) (Stage 2).¹³¹ In **Stage 1**, participants will be randomized at a 1:1:1 ratio to receive one of the three treatments: placebo, citicoline, and pregnenolone. After 99 participants have completed the duration of treatment (completer, dropout, discontinued) an interim analysis will be performed based on the number of drinks per drinking day (primary outcome measure). Based on the interim analysis, adaptations such as stopping the trial early, re-estimating the sample size, or a different randomization scheme may be applied as recommended by the independent DSMB.

Note that a precision analysis (i.e., a confidence interval approach) will be considered for treatment selection at Stage 1.¹³¹ To evaluate the relative risk of making wrong decision and increase confidence in not making wrong decision at Stage 1, sensitivity analyses based on predictive confidence interval of the true difference, which is calculated using the observed difference, at interim analysis will be conducted for treatment selection. At the end of Stage 1, one of the following decisions will be made based on the following principles:

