- 1. The trial will be stopped if neither active treatment appears to be effective (both active treatment effect sizes are smaller than a minimum clinically important difference, defined as an effect size of 0.25).
- 2. The trial will continue to Stage 2, if there is evidence (based on precision analysis i.e., a smaller interval width) that at least one treatment from the interim analysis at end of Stage 1 is more effective than placebo. If both treatments appear to be effective in Stage 1 then the trial will continue with three-arms. Findings from the interim analysis may result in change in sample size required for achieving statistical

significance at a desired power. At the end of Stage 2, data collected from both stages will be combined for a final analysis. Depending on the results of the interim analysis, blinded sample size re-estimation may be performed per recommendation from the DSMB.

Stage 2 will be a two-arm (assuming that only one promising treatment is retained) randomized study comparing the selected treatments from Stage 1 versus the placebo. At the end of the Stage 2, the selected treatment will be compared with placebo using the number of drinks per drinking day as the primary outcome measure. At each stage, the primary efficacy analysis will be performed based on the intention-to-treat (ITT) population, defined as all randomized participants who have at least one follow-up evaluation regardless of their compliance with the protocol. In case of substantial numbers of protocol violations, a per-protocol analysis may be done to determine whether they influence the conclusions. At end of Stage 2 (or end of trial), a clinical superiority test may be performed after non-inferiority has been established, without paying any statistical penalty.

Sample size re-estimation: Sample size re-estimation will be performed based on the number of drinks per drinking day as the primary outcome measure. Sample size calculations will be performed as follows:¹³²

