At Stage 1, we will recruit 99 subjects (i.e., 33 subjects per arm) with 1:1:1 treatment allocation ratio, which provides clinically meaningful minimum *effect size of 0.25 between each treatment arm and placebo with* a two-sided test at the 5% level of significance. After review of interim data, an additional 100 subjects at 1:1 ratio will be recruited at Stage 2. If the effect size for *both* medications is at least 0.50 at interim analysis then we will have 81.4% power with 66 participants per arm and the study will continue with three treatment arms. To summarize: 1) If neither treatment has an effect size of at least 0.25 at interim analysis then the trial is discontinued. *This effect size was selected because it is a clinically meaningful value. Naltrexone has an average effect size of approximately 0.15-0.20 in clinical trials for alcohol dependence.*¹³³ *Thus, a useful new treatment for alcohol dependence should at least have a larger effect size than the standard treatment. This effect size of 0.25 is also an effect size at interim analysis that provides a reasonable likelihood of a significant difference from placebo at study completion assuming some increase in effect size as more participants are*

enrolled and the variance of the data decreases. 2) If one treatment has an effect size of at least 0.25 then the trial continues dropping the less effective treatment (two-arm study of one medication vs. placebo). 3) If both treatments have an effect size of at least 0.50 then neither treatment is dropped and the trial continues as a three-arm trial (both medications vs. placebo). This assumes that the DSMB assessment determines that the selected treatment(s) has an adequate safety and tolerability profile to continue the trial. We anticipate that the interim analysis will take place at approximately month 26 of the study. As an incentive to enroll quickly and avoid prolonging the study, we will mandate that an interim analysis take place by month 34 even if fewer than 99 participants have been enrolled. All interim analysis decisions will be made in consultation with the NIAAA program official and DSMB.

Statistical Methods:

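### Two rules for keeping both drugs after Stage 1 disagree (an implied effect size of 0.25 against a stated 0.50), and interval width is offered as evidence of efficacy

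*Combined protocol and SAP*

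**What the plan says.** Section 3.3.c of the combined protocol and SAP sets out the decision at the end of Stage 1 in two places.

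**General Analytic Plan (decision list).** Item 1 stops the trial if neither drug appears effective, and explains this in parentheses as "both active treatment effect sizes are smaller than a minimum clinically important difference, defined as an effect size of 0.25". Item 2 continues "if there is evidence (based on precision analysis i.e., a smaller interval width) that at least one treatment" is better than placebo, and adds: "If both treatments appear to be effective in Stage 1 then the trial will continue with three-arms". Just before the list, the plan says that "a precision analysis (i.e., a confidence interval approach) will be considered for treatment selection at Stage 1", together with "sensitivity analyses based on predictive confidence interval of the true difference".

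**Sample size re-estimation (numbered summary).** Item 1 repeats the stop rule at 0.25. Item 2 reads: "If one treatment has an effect size of at least 0.25 then the trial continues dropping the less effective treatment". Item 3 reads: "If both treatments have an effect size of at least 0.50 then neither treatment is dropped and the trial continues as a three-arm trial". The section closes with: "All interim analysis decisions will be made in consultation with the NIAAA program official and DSMB".

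Three other places bear on which rule was meant. Section 3.1 (Adaptive Clinical Trial Designs) promises decision rules fixed in advance. Section 3.2 speaks of a powered trial of the more promising drug. Section 3.4 says both drugs may stay if both look especially promising.

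**The concern.** The decision list explains *appears to be effective* as an effect size of at least 0.25 and, one item later, uses the same phrase to keep three arms. The numbered summary asks for 0.50 on both drugs. Observed effects of 0.30 and 0.40 therefore give three arms under the list and two under the summary.

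The rule decides whether Stage 2 has two arms or three, and so the sample size and power of each comparison. If the text is not reconciled beforehand, a result in the disputed region has to be resolved by choosing a reading after the DSMB has had access to unblinded data (3.3.b.11). That is what rules fixed in advance are meant to prevent.

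A separate fault is that item 2 of the list describes a smaller interval width as evidence that a drug beats placebo. It does not say smaller than what, and width does not measure benefit.

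**Working it through.** **Inputs from 3.3.c:** 33 per arm in Stage 1 at 1:1:1; 100 more at 1:1 in Stage 2; 66 per arm if three arms continue; two-sided 5% test; thresholds 0.25 and 0.50. **Assumptions:** outcome roughly normal with SD 1 (the documents give no SD for drinks per drinking day), no dropout, no sample size re-estimation. The true effects are a range chosen for illustration.

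**1. The plan's own figure.** Two-sample t-test, d = 0.50, 66 per arm: noncentrality 0.50 × √(66/2) = 2.872, df 130, power 81.35%. This reproduces the stated 81.4%.

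**2. The two Stage 2 designs.** Two arms: 33 + 100/2 = 83 per arm. Three arms: 66 per arm. Fixed-sample power per comparison:

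| True d | 66 per arm | 83 per arm |
|---|---|---|
| 0.50 | 81.4% | 89.3% |
| 0.40 | 62.6% | 72.6% |
| 0.25 | 29.7% | 36.0% |

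**3. How often the rules differ.** Each observed effect has SE √(2/33) = 0.246. The shared placebo arm gives the two a correlation of (1/33)/(2/33) = 0.5. With Φ₂ the bivariate normal distribution function,

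P(both ≥ c) = Φ₂((δ₁ − c)/0.246, (δ₂ − c)/0.246; 0.5).

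The rules differ with probability P(both ≥ 0.25) − P(both ≥ 0.50). For true effects 0.25/0.25, the first term has both arguments at 0 and equals 1/3. The second has both at −0.25/0.246 = −1.016 and equals 6.0%. The difference is 27.3%.

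| True effects | Both ≥ 0.25 | Both ≥ 0.50 | Designs differ |
|---|---|---|---|
| 0 / 0 | 6.0% | 0.4% | 5.7% |
| 0.25 / 0 | 12.5% | 1.2% | 11.2% |
| 0.50 / 0 | 15.2% | 1.9% | 13.2% |
| 0.25 / 0.25 | 33.3% | 6.0% | 27.3% |
| 0.50 / 0.25 | 47.0% | 12.5% | 34.5% |
| 0.50 / 0.50 | 75.1% | 33.3% | 41.7% |

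Differences are taken before rounding. A simulation that estimated the SD in each trial moved them by 0.7 points or less. If the numbered summary governs, every entry in the last column is 0%.

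**4. Interval width.** For a difference in means at 33 per arm, the 95% interval has width 2 × 1.998 × s × √(2/33) = 0.98s. The observed effect does not enter. On the effect-size scale (inverting the noncentral t, df 64) the width is 0.965 at d = 0, 0.969 at 0.25 and 0.980 at 0.50, so it is slightly wider when the drug works.

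**The case against.** The best reply is that there is only one rule. The numeric version is introduced as a summary in the same section, repeats the stop rule, and comes after an earlier sentence that already ties three arms to 0.50 for both drugs. The list calls its contents principles, and 3.2 and 3.4 fit the higher bar. This largely stands: the 0.50 rule is probably the intended one. But no sentence says that it governs or that it defines the list's wording, and the list attaches 0.25 to the same phrase one item earlier.

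Second, the practical harm is limited. This also stands. Given a result in the disputed region, simulation with true effects 0.25/0.25 gives at least one significant drug in 67% of trials with three arms and 63% with two. At 0.50/0.50 it is 95% for both. What two arms gain is power for the selected drug: 63%, against 48% per drug with three arms, at 0.25/0.25.

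Third, the width remark may be only a clumsy gloss on the confidence interval approach. That may be so; the repair is a change of wording.

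A reader might go further and take the list to require a 95% interval that excludes zero. At 33 per arm this needs an observed effect of about 0.49, so best effects from 0.25 to 0.49 would meet neither the stop nor the continue rule. The documents do not support this. They state no such criterion, they say only that an interval approach will be considered, and the sample size text explains why 0.25 is enough to continue.

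**Conclusion.** The concern holds as an inconsistency in a decision threshold. Read literally, the two parts of 3.3.c lead to different Stage 2 designs in 5.7% to 41.7% of trials over the true effects examined, and in none if the numbered summary governs. These figures rest on 33 per arm, a normal outcome, a shared placebo arm and no dropout. The width remark is invalid as a criterion for efficacy, whichever rule was meant.

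A reader might infer inflated type I error; that is not shown. In simulation with no true effect, the 0.25 stop treated as binding and unadjusted final tests at two-sided 5%, the chance of any false positive was about 3.1% under the 0.50 rule and 3.5% under the 0.25 reading. Nor is there a demonstrated loss in the chance of finding at least one effective drug. The stop rule is the same in both places. Severity is minor to should-fix: easily corrected, and worth correcting before unblinded data are reviewed.

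**What to change.** Before the interim analysis, amend 3.3.c as follows, using only the plan's own thresholds:

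- In the decision list, state that the thresholds under Sample size re-estimation are the decision rule. Stop if both effects are below 0.25. Keep three arms only if both are at least 0.50. Otherwise the drug with the larger observed effect continues against placebo, subject to the DSMB safety review already planned.
- In item 2 of the numbered summary, write *at least one treatment*, so that a result such as 0.30 and 0.40 is clearly covered.
- Delete the words that equate precision analysis with a smaller interval width.
- State that the confidence and predictive intervals are supportive sensitivity analyses and do not replace the thresholds.

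The cost is a few sentences, with no change in sample size. It is not purely editorial: it settles that the intervals do not decide selection, and it leaves the DSMB slightly less latitude. The risk of dropping a useful drug, which 3.4 accepts, remains. The edit also does not define the effect size itself (which SD, which time point, how it comes from the GEE model); the sponsor would need to state that for the rule to be fully operational.

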3.2. Innovation

Alcohol dependence is very common in BPD and schizoaffective disorder. However, literature on the treatment of these dual-diagnosis populations is quite limited. Thus, the patient population studied is innovative. The drugs tested are also innovative. Each is a dietary supplement with interesting clinical and preclinical properties. In addition, the two treatment options have different mechanisms of action that are relevant to alcohol use disorders and BPD/schizoaffective disorder but have not been the focus of extensive attention. Thus, the proposal is consistent with the NIAAA goal to "Discover, develop, and test new, more effective agents to prevent or reduce drinking" (NOT-AA-14-008). The 2-site clinical adaptive trial design is innovative. Adaptive designs are widely used in some areas of medicine, and are currently being explored in the drug abuse field,¹⁰⁶ but, to our knowledge, have not been used in alcohol research. The design allows for the testing of two treatments as well as an adequately powered trial of the more promising option. The stopping rules are also innovative. If neither of the treatments appears promising, the trial will be stopped. This approach decreases the investment of time and resources should the treatments appear to not be very

effective. If an option is promising then the timeframe for drug development will be faster than with current approaches. We suggest that this approach is consistent with the objective of NIAAA to conduct more efficient clinical trials with novel methodology,¹⁰⁹ and with the specific PA. *Finally, we include an exploratory analysis that will examine, with both medications, whether changes in alcohol use occur before or after changes in alcohol craving, mood or cognition. To our knowledge, such an analysis has not been reported in dual BPD/schizoaffective disorder and alcohol use clinical trials. The findings will help inform whether the effects of the medications on alcohol use are driven by improvement in craving and other clinical outcomes.*

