The primary analysis is to assess between-group differences in alcohol use measures including drinks per drinking day (primary outcome measure), heavy drinking days, and drinking days using Generalized Estimation Equations (GEEs) analysis with a site effect as a cluster. GEE model has been used in a prescription drug abuse treatment study with multiple site adaptive design (Weiss et al., 2010).¹⁰⁶ Point estimates of the difference in the average of the number of drinks per drinking day between treatment groups and their corresponding 95% confidence intervals will be obtained. A similar analysis will be used to assess exploratory aims 1 (mood), 2 (side effects), and 3 (craving). Length of time in the study in weeks will be compared between groups using Cox proportional hazards regression (SAS Proc PHREG). Assessments only obtained at baseline and weeks 6 and 12 (e.g. GGT, AST, ALT and CDT levels) or baseline and week12 (e.g. cognitive assessments, neurosteroid and choline levels) will be analyzed using analysis of variance (ANOVA). The correlation between the reduction in alcohol use/alcohol craving and reduction in manic and depressive symptoms, and also improvement in cognitive outcomes, will be assessed using Pearson's or Spearman's correlation coefficient. To address exploratory aim 6) "Determine whether changes in alcohol craving, mood or cognition occur before or after changes in alcohol use." a panel model with lagged effects¹³⁴ will be used to analyze 12-week longitudinal data (SAS Proc Panel) in order to explore serial correlations between changes in alcohol use and depressive symptoms or cognitive outcomes with lagged effect (e.g. one week, two week). The panel model will be constructed for each alcohol use, alcohol craving, depressive and manic symptom, and cognitive outcome and test if change in alcohol use follows changes in craving, mood or cognition at subsequent visits and vice versa.

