At each stage, a table will show the adverse events (categorized by seriousness, severity, and possible association with study drug) ordered by decreasing frequency for all patients. If appropriate, the incidence rate of adverse events will be compared by Fisher's Exact Test. Special attention will be given to those participants who have discontinued due to adverse events or experienced a serious adverse event. Exploratory analyses such as determining if baseline blood neurosteroid or choline levels predict response and whether changes in these levels are associated with clinical response will be conducted using a mixed model (SAS Proc GLIMMIX) with baseline blood neurosteroid and choline levels as fixed effects. In addition, subgroup analyses with respect to patient demographics and characteristics may be performed as deemed appropriate by the PI and/or biostatistician. Unless otherwise noted, tests of hypotheses are 2-sided and the nominal level of significance will be 0.05.

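### The better drug is picked on Stage 1 and both stages are pooled at an unadjusted 0.05: with two inert drugs, any false claim of benefit has a chance of about 3.1% with the 0.25 stop obeyed, against a joint 2.5%

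*Combined protocol and SAP*

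**What the plan says.** All references are to section 3.3.c unless stated.

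- **Selection.** Stage 1 randomizes 99 people, 33 per arm, to placebo, citicoline or pregnenolone. Under Sample size re-estimation, if one drug reaches an effect size of 0.25, "then the trial continues dropping the less effective treatment".
- **Pooling.** The General Analytic Plan says: "At the end of Stage 2, data collected from both stages will be combined for a final analysis". The outcome is drinks per drinking day at both looks.
- **Final inference.** Statistical Methods plans point estimates of the difference "between treatment groups and their corresponding 95% confidence intervals will be obtained", and says that "tests of hypotheses are 2-sided and the nominal level of significance will be 0.05". No adjusted critical value, combination test, closed testing or alpha spending appears.
- **The stop.** The wording is mostly firm: "If neither of the treatments appears promising, the trial will be stopped" (section 3.2) and "The trial will be stopped if neither active treatment appears to be effective" (General Analytic Plan, principle 1, which ties this to 0.25). But the General Analytic Plan introduces the adaptations in permissive terms, on the DSMB's recommendation, and Sample size re-estimation makes interim decisions a matter of consultation.
- **Three arms.** General Analytic Plan, principle 2: "If both treatments appear to be effective in Stage 1 then the trial will continue with three-arms". Sample size re-estimation: "If both treatments have an effect size of at least 0.50 then neither treatment is dropped". The first has no threshold of its own; principle 1 suggests 0.25.
- **Precision gate.** Principle 2 also asks for evidence from a precision analysis before Stage 2, without a criterion.

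**The concern.** The trial is built to end with a claim about whichever drug looked better at the interim. Choosing between two drugs gives chance two tries, and pooling carries a lucky Stage 1 result into the final test. An ordinary 1.96 cutoff does not allow for that.

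The stop pulls the other way on error, because it ends most null trials. But it also means that the trials which continue are those with a favourable Stage 1 result, so the ordinary estimate and interval lose their nominal properties. How large both effects are depends on rules that the plan states in two ways or leaves undefined.

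**Working it through.** **Inputs.** 33 per arm at Stage 1; 100 more at 1:1, so 83 per arm after pooling; 66 per arm if three arms continue; stop below 0.25; two-sided 0.05 (all from 3.3.c). Assumed: normal outcome, known SD of 1, no dropout, fixed sizes, no efficacy claim at the interim, no precision gate.

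**1. The plan's own figure.** Effect size 0.50 with 66 per arm and a two-sided 0.05 t-test gives 81.4% power, as printed. At 0.025 per comparison it would be 72.7%. So the stated power assumes no correction for two drugs.

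**2. Hand check of selection alone** (always two arms, no stop, both drugs inert). The two Stage 1 z-values share a placebo, so their correlation is 0.5.
- Mean of the larger: √(0.5/π) = 0.399. Variance: 1 − 0.5/π = 0.841.
- Pooled z = √(33/83)·z₁ + √(50/83)·z₂ = 0.631·z₁ + 0.776·z₂.
- Mean: 0.631 × 0.399 = 0.252. Variance: 0.398 × 0.841 + 0.602 = 0.937, so SD 0.968.
- P(z > 1.96) ≈ 1 − Φ((1.96 − 0.252)/0.968) = 1 − Φ(1.76) ≈ 3.9%. Simulation gives 3.90%.
- Bias from selection alone: 0.252 × √(2/83) = 0.252 × 0.155 ≈ 0.04 SD.

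**3. Full rules, both drugs inert** (simulation, millions of trials per scenario). With the 0.50 three-arm rule, 75.1% of trials stop, 24.5% go to two arms and 0.4% keep three.

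| Three arms if both reach | 0.25 stop | Any false benefit | Either direction | Per drug | Cutoff giving 2.5% | False benefit at z 2.21 |
|---|---|---|---|---|---|---|
| 0.50 | obeyed | 3.1% | 3.1% | 1.6% | 2.07 | 1.8% |
| 0.50 | never enforced | 4.0% | 5.1% | 2.0% | 2.16 | 2.2% |
| 0.25 | obeyed | 3.5% | 3.5% | 1.9% | 2.13 | 2.1% |
| 0.25 | never enforced | 4.4% | 5.5% | 2.4% | 2.21 | 2.5% |

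With one drug and no selection, false benefit is 1.8% with the stop and 2.5% without. On the 0.50 rule, choosing between two therefore adds 3.1 − 1.8 = 1.3 or 4.0 − 2.5 = 1.5 points. The value 2.21 is the Dunnett cutoff for two drugs and a shared placebo.

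**4. Precision gate** (0.50 rule, stop obeyed). If the gate means that the interim lower bound must exceed zero, false benefit is 2.6% (one-sided 90% bound), 1.9% (one-sided 95%) or 1.3% (two-sided 95%).

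**5. Other sensitivities** (stop obeyed / never enforced). A 30% loss in every arm, the limit of the completion rate expected in 3.3.d, gives 3.4% / 4.1% on the 0.50 rule and 3.8% / 4.5% on the 0.25 reading. An early interim, assumed at 24 per arm, gives 3.1% / 3.9% on the 0.50 rule.

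**6. Naive estimate in continuing two-arm trials** (0.50 rule, stop obeyed). The bias is +0.15 SD at truth 0 (interval coverage 88%), about +0.08 SD at 0.25 and +0.03 SD at 0.5. One drug with the same stop and no selection gives +0.150, +0.078 and +0.028 SD, with coverage of 88.5%, 95.0% and 96.2%. So the stop is the source.

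**The case against.** The plan prints a two-sided 5% level and nothing about joint error over two drugs. A reader might infer from unadjusted selection and pooling that the trial breaks its own 5% level, or that each drug is tested too liberally. The documents do not support either in general. With the stop obeyed, total two-sided error is 3.1% (0.50 rule) or 3.5% (0.25 reading), below 5%. It passes 5% only if the stop is never enforced (5.1% or 5.5%), and the text favours a firm stop. Per-drug error is below 2.5% on every reading. The drugs have different mechanisms, and Stage 2 is described as early confirmation, so joint control is a choice that can be argued either way.

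The precision gate is a stated condition, and a strict version would take the error to 2.5% or less on the 0.50 rule. That objection stands as a limit on the size. It does not settle the matter, because the gate has no criterion, and a one-sided 90% bound still leaves 2.6%.

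The cutoffs also presume a test that holds its nominal level. Statistical Methods plans GEE with site as the cluster, at two sites. Any problem with that variance estimate is separate, and a larger critical value does not repair it.

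Finally, one sentence calls sample size re-estimation blinded, which would weaken the case for a combination test. A nearby sentence lets interim findings change the size, so the point is open.

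**Conclusion.** The concern holds, and its size is modest. With two inert drugs, the chance of at least one false claim of benefit is about 3.1% on the better-supported reading (stop obeyed, three arms only at 0.50). That is 0.6 points above a joint 2.5%. On the other readings it is 3.5% to 4.4%, an excess of 1.0 to 1.9 points. A reader might take 4.0% as a ceiling; it is only the value for the 0.50 rule without the stop.

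The benchmark is the benefit side of a two-sided 5% test applied jointly to both drugs, adopted for this review. The figures also rest on normality, fixed sizes, no interim efficacy claim, no precision gate, and a final test that holds its level.

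A reader might also blame selection for the favourable estimate. The calculation points to the 0.25 stop: selection alone adds at most about 0.04 SD. The poor coverage of 88% is at truth 0, among the roughly 25% of null trials that continue with two arms; coverage is near nominal at 0.25 and 0.5.

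What needs action is that the final test and interval lack their nominal properties under the plan's own rules, and that the two three-arm rules conflict.

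**What to change.** Before the interim, amend the SAP to:

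1. **State the error standard**, for example at most 2.5% for any false claim of benefit.
2. **Settle the rules.** Reconcile the two three-arm rules, say whether the 0.25 stop is binding, and define or remove the precision gate.
3. **Prespecify a final test that meets the standard under those rules.** With fixed Stage 2 sizes and a test that holds its level, z 2.21 keeps false benefit at or below 2.5% on all four readings. The smaller cutoffs (2.07 to 2.16) apply only if the matching rules are fixed. With 30% loss, 2.07 becomes 2.11, and 2.21 still holds 2.0% to 2.5%.
4. **If Stage 2 size may depend on the unblinded interim effect**, use a closed inverse-normal combination test with fixed weights √(33/83) and √(50/83). Use Dunnett-adjusted intersection p-values at Stage 1, and also at Stage 2 whenever three arms continue. Adjusting Stage 1 alone leaves 2.8% on the 0.25 reading without the stop; adjusting both gives 2.5%.
5. **Report an estimate adjusted for the stop and selection** beside the naive one.

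**Cost.** Wording, no extra participants, and some power. Below, power is for the active drug at true effects 0.5/0 and 0.25/0, and for any claim at 0.25/0.25:

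| Rules and cutoff | 0.5/0 | 0.25/0 | 0.25/0.25 |
|---|---|---|---|
| 0.50 rule, binding, z 2.07 | 79.1% to 77.8% | 27.1% to 24.7% | 40.0% to 36.7% |
| 0.50 rule, binding, z 2.21 | 79.1% to 75.7% | 27.1% to 21.6% | 40.0% to 32.5% |
| 0.25 reading, not enforced, z 2.21 | 88.6% to 83.3% | 34.4% to 26.0% | 47.4% to 37.0% |

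The loss runs from about 1 to 10 points. It is smallest with the stop binding and a true effect of 0.5.
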